# AMENDMENTS TO THE INITIAL PROTOCOL

Modification	Pattern	Protocol version
Amendment 1	Pharmacy chapter clarification	2.0 of 02/22/2018
Amendment 2	Co-investigator update	2.0 of 02/22/2018
Amendment 3	Blind box allocation and co-investigator	3.0 of 05/24/2018
	update	
Amendment 4	Co-investigator update	3.0 of 05/24/2018
Amendment 5	NIFC update	3.0 of 05/24/2018
Amendment 6 Addition of a center + extension of the		4.0 of 07/25/2019
	inclusion period (18 months)	

# **Summary**

Title	RHIZ'ART – The effects of infiltration with hyaluronic acid and			
	corticosteroids on pain versus corticosteroids alone in			
	rhizarthrosis.			
Developer	CHD Vendée La Roche sur Yon			
Coordinating Investigator	[name] [name], CHD Vendée			
Protocol version	4.0 du 25/07/2019			
Justification / context	Rhizarthrosis, or arthrosis of the trapeziometacarpal joint, is a common			
	form of osteoarthritis that affects 10-25% of women, particularly after			
	menopause. It affects unstable joints that are subject to significant pressure.			
	It progresses over several years and can lead to a Z-shaped deformity			
	of the thumb column, which is functionally disabling.			
	Treatment consists of a combination of non-pharmacological measures			
	such as relative resting of the joint, resting orthoses and icing, with			
	pharmacological measures such as analgesics, oral or local non-			
	steroidal anti-inflammatory drugs, or even cortisone or hyaluronic acid			
	infiltrations.			
	To date, no study has tested the benefit of combining cortisone and hyaluronic acid in rhizarthrosis. In view of the current literature, we			
	propose conducting a two-arm study, with corticosteroids as the			
	reference arm and hyaluronic acid combined with cortisone as the			
	experimental arm.			
Main objective	To compare the efficacy of corticosteroid infiltration alone to			
	corticosteroid infiltration combined with hyaluronic acid in			
	patients with rhizarthrosis at 3 months.			
Secondary Objectives	- Comparison of the changes in pain with activity at M1, M6 and			
	M12; and of the most intense pain.			
	- Comparison of pain between M0 and M3, by weekly recordings			
	of VAS (in a notebook given to the patient).			
	- Comparison of the changes in pain at rest at M0, M1, M3, M6			
	and M12; and of the most intense pain.			
	- Comparison of the changes in function with the Cochin hand			
	scale at M1, M3, M6 and M12.			
	- Comparison of grip and opposition strength changes at M1,			
	M3, M6 and M12.			
	- Description of ultrasound changes.			
	- Comparison of injection pain.			
	- Comparison of the patient's perception of changes in pain at 3			
	months.			
	- Comparison of new infiltrations.			
	- Description of adverse effects and events.			
	- Description of analysis and NSAID use.			
	Description of analgesic and INSAID use.			

	- Comparison of the after-effects of infiltration.			
Primary endpoint	The primary endpoint for evaluating the efficacy of rhizarthrosis			
v 1	infiltration was the intensity of pain at the base of the thumb (as			
	defined by the patient, i.e., during activity) on the Visual Analogue			
	Scale (VAS) of pain at baseline and at 3 months in the 2 groups.			
Secondary endpoint	- Recording VAS during activity			
secondary enupoint				
	- VAS for pain perceived at the base of the thumb at rest			
	- The worst pain score			
	- Cochin score			
	- Grip and opposition strength			
	- Ultrasound evaluation at inclusion and M3			
	- VAS during infiltration			
	- Verbal score for overall change at 3 months.			
	- Number of corticosteroid infiltrations			
	- Recording adverse effects and events			
	- Recording data on analgesic and NSAID use			
	- Number of days off work from the start of orthosis use			
	- Possible progression to a surgical procedure			
	Table 1 Section 1 m Section Processing			
Methodology / Study	- Phase IV drug trial			
diagram	- Regional multicenter study (CHU Nantes, CHD Vendée, CHG Le			
	Mans)			
	- Comparative, Randomized, Controlled, Superiority			
	- Control group: reference drug (Diprostene®)			
	- Double-blind (patient and primary endpoint assessor)			
	- With 2 groups compared: one receiving corticosteroids (CTC) and			
	0.9% NaCl; the other receiving a combination of Hyaluronic Acid			
	(HA) and CTC			
	- In 2 parallel groups			
Inclusion Criteria	- Adults, ≥ 40 years			
	- Pain at the base of the thumb (near the wrist) triggered by			
	direct pressure and movement			
	- Pain resistant to well-conducted medical treatment, with			
	analgesics, NSAIDs and icing, with a VAS $\geq$ 4 for more than 3 months.			
	- Radiological lesions (Kapandji view; anterior + profile)			
	typical of rhizarthrosis, Eaton and Litter stage II or III, with at			
	least 2 of the following 5 radiological features observed on the			
	trapeziometacarpal joint:			
	trapeziometacarpai joint: -marginal osteophyte			
	-pinching of the joint space			
	-subchondral sclerosis			
	-subchondral geode			
	-absence of osteopenia			
	- Patient capable of understanding the protocol and having			
	signed an informed consent form			
	- Patient with social security coverage			

N. I. I. C.	TZ 11			
Non-Inclusion Criteria	- Known allergy to one of the products (Diprostene® or			
	Sinovial®) including the excipients (methyl			
	parahydroxybenzoate, propyl parahydroxybenzoate, benzyl			
	alcohol).			
	- Change in analgesic treatment in the 4 weeks prior to inclusion.			
	- Patients with symptomatic bilateral rhizarthrosis			
	- Scaphoidotrapezial osteoarthritis			
	- Local or general infection			
	-Severe coagulation disorders, ongoing anticoagulant therapy			
	- Severe and/or uncontrolled hypertension			
	- Previous local surgery			
	- Associated inflammatory rheumatism			
	- De Quervain's tendinopathy, thumb with associated protrusion			
	- Previous infiltrations less than 6 months old			
	- Uncontrolled diabetes			
	- Live vaccines			
	-Severe cases of water and/or sodium retention (hypernatremia),			
	particularly in heart failure, decompensated liver disease (edema			
	and ascites)			
	- Pregnant or breast-feeding women			
	- Immunocompromised or hemodialysis patients			
	- Patients under guardianship or deprived of their liberty			
	- Patients participating in another clinical research protocol			
	involving a drug or medical device			
	- Patients unable to follow the protocol, as judged by investigator			
Treatments / Strategies /	HA + CTC arm: 0.5ml Diprostene® and 0.5ml Sinovial mini®.			
Procedures	CTC + Na Cl 0.9% arm: 0.5 ml Diprostene® and 0.5 ml NaCl 0.9%.			
Number of patients	A total of 150 patients			
Search duration	Length of inclusion period: 36 months			
	Duration of participation for each patient: 12 months			
	Total study duration: 48 months			
Expected benefits	Optimization of the management of patients suffering from			
	rhizarthrosis			

# List of abbreviations

CMC OA	Carpometacarpal (base of the thumb) Osteoarthritis
НА	Hyaluronic Acid
MA	Marketing Authorization
CRA	Clinical Research Associate
GCP	Good Clinical Practice
EC	Ethics Committee
CNIL	Commission Nationale de l'Informatique et des Libertés (French
CNIL	Data Protection Authority)
CRF	Case Report Form (observation booklet)
CTC	Corticosteroids
SAE	Serious Adverse Event
SAR	Serious Adverse Reaction
SUSAR	Unexpected Serious Adverse Reaction
IDE	State-qualified nurse
SmPC	Summary of Product Characteristics

### 1. General information

#### 1.1. Title

The effects of infiltration with hyaluronic acid and corticosteroids on pain versus corticosteroids and saline in rhizarthrosis. **RHIZ'ART**.

# 2. Scientific rationale and general description of the research project

# 2.1. Name and description of investigational drug(s)

We will be using two commonly used products: the drug Diprostene® (Betamethasone) and the medical device Sinovial mini®.

These are described in detail in Chapter 6.

# 2.2. Summary of the results of available non-clinical trials and clinical trials relevant to the biomedical research in question

Rhizarthrosis, or arthrosis of the trapeziometacarpal joint, is a common form of osteoarthritis that affects 10-25% of women, particularly after menopause. It affects unstable joints that are subject to high pressure. It is often bilateral, with frequent asymmetry of clinical and radiological involvement. Pain is located at the anatomical snuffbox, with fluctuating progression and no correlation between radiological and clinical severity. It progresses over several years and can lead to a Z-shaped deformity of the thumb column, which is functionally disabling.

Treatment combines non-pharmacological measures, such as relative resting of the joint, rest orthoses, icing, etc., with pharmacological measures such as analgesics, oral or local non-steroidal anti-inflammatories, or even cortisone or hyaluronic acid infiltrations. The European League Against Rheumatism's (EULAR) recommendations for digital osteoarthritis state that "intra-articular delayed corticosteroid infiltration is effective in painful flare-ups of digital osteoarthritis, particularly of the trapeziometacarpal joint". Both products have been granted marketing authorization, but only corticoids are eligible for reimbursement.

However, no methodologically rigorous studies have tested these infiltrations versus placebo. Only Meenagh has conducted this type of study, but on a small number of patients (2 groups of 20 patients) with small volumes injected (0.25 ml); with no difference noted between the placebo and corticosteroid groups. 

On the other hand, these two types of infiltration have been compared, with both showing efficacy on pain and function.

In 2005, Stahl conducted a randomized study to compare the efficacy of corticosteroid infiltration (CTC) versus hyaluronic acid (HA) and found a reduction in pain in both groups at one month, which was maintained at 6 months. On the other hand, hyaluronic acid infiltration improved functional capacity as early as 3 months and the improvement lasted longer than with corticosteroids.

In 2006, Fuchs reported similar results, with improvement in pain and function for both types of infiltration in a randomized study of 56 patients. Pain improvement was faster with corticosteroids (significant at 2 weeks) but slightly better with HA at 26 weeks, with a clearer functional gain for HA mainly at 6 months.

In 2008, in a 3-arm study, one of which was placebo, Heyworth made the same findings but with no significant difference with placebo. He noted an improvement in pain and function in

all 3 groups (18 to 22 patients in each), with a clearer improvement in pain for the HA group at 6 months and in function at 3 and 6 months.

Moreover, the latest study in 2015 by Montfort, concludes that "HA was more effective over time and improved functional status more markedly in patients with severe symptoms".

Concerning the number of HA infiltrations to be administered in rhizarthrosis, a French team led by Roux C showed that there was no difference between groups receiving one, two or three infiltrations at one-week intervals, in terms of neither pain nor function.

Therefore, the 2 types of infiltration appear to be effective, but with different response profiles: corticoids have a rapid analgesic and anti-inflammatory action, whereas HA has a more delayed and sustained action over time. Consequently, it seems appealing to combine these 2 treatments to obtain a synergistic effect. One study demonstrated the benefits of this combination in gonarthrosis, which was more effective on pain than hyaluronic acid alone and there was no difference in functional improvement between the two groups.

Some authors have questioned the potential clinical or histological risks of combining these two drugs, given the risk of reduced chondrocyte proliferation and increased apoptosis which could lead to chondral degradation. However, no increased risks have been reported with this combination, neither clinically nor histologically.

To date, no study has tested the benefit of combining cortisone and hyaluronic acid in rhizarthrosis. In view of the current literature, and following a meta-analysis published in May 2016, which echoed these results and concluded that "the synergy of these two drugs should be explored further [...]. Further comparative trials involving a larger number of patients would be useful" we propose answering this question by conducting a two-arm study, one reference arm with cortisone and placebo and the other with a combination of hyaluronic acid and cortisone.

# 2.3. Summary of the benefits, if any, and of foreseeable and known risks to persons undergoing research

#### 2.3.1. Benefits

#### 2.3.1.1. Individual benefits

The research participants can expect to benefit individually from the analgesic action of the product(s) proposed for this pathology, as well as a limitation of the disability.

This benefit will be objectively assessed both directly by the participant and by an external medical assessment based on a pain scale.

#### 2.3.1.2. Collective benefit

A collective benefit of rhizarthrosis management optimization can also be envisaged from this research, with a reduction in work stoppages.

#### 2.3.2. Risks

#### 2.3.2.1. Individual risk

# Risks and physical constraints

## Risks associated with protocol treatments:

Betamethasone (Diprostene®) has a marketing authorization for this indication, and the risks associated with its administration are listed in the SmPC: these are mainly local reactions but flushing and anaphylactic or anaphylactoid reactions are also possible.

Systemic complications of corticosteroid therapy are unlikely, given the dose administered and the low systemic uptake.

Hyaluronic acid (Sinovial mini®) is a CE-marked medical device for which the complications are listed in the instructions for use. Hyaluronic acid AEs are mainly local reactions (pain, inflammation, etc.).

The injection of 0.9% NaCL presents no particular risk in terms of salt intake, given the small quantity injected.

Intra-articular administration entails a risk of pain during injection, minimal bleeding or local hematoma following injection, and a risk of infection, but these can be prevented by aseptic measures/good practice during preparation and administration. Intravascular injection is prevented by adherence to good injection practices.

A local reaction to the ultrasound gel is possible. A reaction to the latex used for the sterile ultrasound protector is also possible.

Adverse events are detailed in section 8-Safety assessment. Reference documents (SmPC-notice) are appended to the protocol.

Other constraints directly related to research include:

- Recording pain and any adverse effects in a patient diary on a weekly basis for the first 3 months after the procedure.
- Answering a questionnaire to obtain the Cochin score and the verbal global evaluation scale.
- Follow-up visits scheduled as part of the protocol at 1, 3, 6 and 12 months.

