### 4.2.2.2. Ultrasound-guided infiltration technique

Infiltrations will be performed on each site in a standardized manner.

The patient is placed in a supine position with arms extended at the side of the body, hands resting on a hard surface, and the palm of the hand to be infiltrated facing upwards.

The reference section is the longitudinal section of the palmar aspect of the joint. The trapeziometacarpal joint is identified as the hypoechoic zone between the 2 bones.

The joint is approached perpendicularly to the probe: the approach is generally lateral to medial but can be easily performed in the other direction depending on the patient's position and the operator's experience. In this technique, the needle appears as a hyperechoic point with a comettail artefact. The needle is introduced perpendicularly to the probe at an angle of 30° to 45° until the hyperechoic spot appears. A 25 G subcutaneous needle is used, with local anesthesia using Xylocaine for the subcutaneous planes and passage of the capsule.

The criterion for success is that the infiltration is performed without resistance, with distension of the capsule observed on ultrasound.

This technique was chosen because it allows intra-articular verification as shown by Di Sante who administered intra-articular injections of hyaluronic acid using a perpendicular approach to the probe, and in 100% of the patients obtained a bulging appearance of the capsule after injection, indicating the intra-articular localization of the product. 

Similarly, in an anatomical study, Umphrey et al demonstrated the intra-articular localization of the infiltration product by arthrography in 17 cadavers, with 16 (94%) actually having had an intra-articular injection. 

Depending on the randomization arm, either 0.5 ml of CTC and 0.5 ml of 0.9% NaCl; or 0.5 ml of CTC and 0.5 ml of HA will be injected.

During these infiltrations, a sterile drape will be placed vertically on an infusion stand, to ensure patient "blinding".

Therefore, the operator will not be blinded; but this doctor will not be the evaluating doctor, who will be effectively blinded to the product(s) injected.

Each infiltration will be followed, if necessary, by a 48-hour work stoppage in accordance with standard practice.

Each patient will be fitted with a resting orthosis for use at night.

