#### 5.2. Non-inclusion criteria

- Known allergy to one of the products (Diprostene® or Sinovial mini®) including the excipients (methyl parahydroxybenzoate, propyl parahydroxybenzoate, benzyl alcohol).
- Change in analgesic treatment within 4 weeks prior to inclusion (change of product and/or dosage).
- Patients with symptomatic bilateral rhizarthrosis
- Scaphoidotrapezial osteoarthritis
- Local or general infection
- Severe coagulation disorders, ongoing anticoagulant therapy
- Severe and/or uncontrolled hypertension
- Previous local surgery
- Associated inflammatory rheumatism
- De Quervain's tendinopathy, thumb with associated protrusion
- Previous infiltrations less than 6 months before
- Uncontrolled diabetes
- Live vaccines

- Severe cases of water and/or sodium retention (hypernatremia), particularly in heart failure, decompensated liver disease (edema and ascites)

- Pregnant women \* or nursing mothers
- Immunocompromised or hemodialysis patients
- Patients under guardianship or deprived of their liberty
- Patients participating in another clinical research protocol involving a drug or medical device
- Patients unable to follow protocol, as judged by the investigator

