# 5.4.1. Criteria and procedures for premature discontinuation of treatment or exclusion of a person from research

The study products are administered in a single dose with two syringes on the day of the initial infiltration (regardless of the randomization arm).

Therefore, in principle, there is no reason to discontinue treatment prematurely, except in the event of a reaction (such as an allergic reaction) during the injection, in which case the treatment should be stopped.

If it has not been possible to administer all the products in the patient's randomization arm, this information will be recorded in the CRF. Protocol visits will nevertheless continue.

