### Administration

#### 1/ Diprostene®:

- infiltration according to GCP of 0.5 ml under ultrasound control
- preparation by the IDE in charge of the study

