#### 2/ Sinovial® mini:

- -Infiltration according to GCP of 0.5 ml under ultrasound control
- preparation by the IDE in charge of the study

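### The protocol names latex in the sterile ultrasound cover as a possible cause of reaction, but neither the eligibility criteria nor the injection technique contains a latex-specific precaution

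*Combined protocol and SAP*

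**What the plan says.** Among the risks in section 2.3.2.1, after a local reaction to the gel, the protocol states: "A reaction to the latex used for the sterile ultrasound protector is also possible".

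The only allergy item among the non-inclusion criteria in 5.2 is "Known allergy to one of the products (Diprostene® or Sinovial mini®) including the excipients", followed by three named excipients. The Summary carries the same item, beginning "Known allergy to one of the products (Diprostene® or".

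Section 4.2.2.2 sets out the technique in some detail: patient position, reference section, angle of approach, drape, needle and anesthetic. For the last two it says: "A 25 G subcutaneous needle is used, with local anesthesia using Xylocaine for the subcutaneous planes and passage of the capsule". It does not mention the probe cover.

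Ultrasound guidance applies in both arms. Section 6.1.1 specifies for Diprostene, which every patient receives, "infiltration according to GCP of 0.5 ml under ultrasound control", and for Sinovial mini "Infiltration according to GCP of 0.5 ml under ultrasound control". The Summary gives the planned size as "A total of 150 patients".

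On allergic reactions in general, 5.4.1 says there is no reason to discontinue treatment early "except in the event of a reaction (such as an allergic reaction) during the injection, in which case the treatment should be stopped".

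**The concern.** The sponsor identified a hazard of the procedure itself and then did not carry it into the sections that decide who is treated and how. Section 2.3.2.1 links infection to asepsis and intravascular injection to good injection practice. It links the latex risk to nothing.

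What is at stake is a small, avoidable risk to any participant who already knows that he or she is allergic to latex. Nothing statistical is at stake. The cover is part of the guided procedure in both arms, so the omission does not favor either one, and it does not touch the sample size or the analysis of the 3-month VAS.

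**Working it through.** No figure in the plan depends on this point, so there is nothing to recompute. The check sets the relevant sections side by side and asks of each whether it contains a precaution that concerns latex.

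1. **Risk statement (2.3.2.1).** Names latex as the material of the sterile cover and says that a reaction can occur. This is the only mention of latex in the text available.
2. **Inclusion criteria (5.1).** No allergy item.
3. **Non-inclusion criteria (5.2 and Summary).** Section 5.2 has 19 items. One concerns allergy, and it is limited to the two products and their excipients. Items naming latex: 0.
4. **Injection technique (4.2.2.2).** Cover material specified: none. Latex question or check: none.
5. **Product precautions and concomitant treatments (6.1.1, 6.2).** Silent on latex.
6. **Randomization (4.3.1).** The investigator confirms, yes or no, that the criteria are met and that consent is signed. Since no criterion mentions latex, this step cannot identify the patient.
7. **Expected adverse events (8.2).** The list for preparation and administration has no latex reaction, although 2.3.2.1 refers the reader to section 8 for detail.

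The general provisions that could protect a latex-allergic patient are these:

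| Provision | Where | Can act before contact? | Specific to latex? |
|---|---|---|---|
| History at the pre-inclusion visit | Study schedule, under 4.2.2.3 | Yes | No |
| Investigator may end participation in the patient's interest | 4.6.1 | Yes | No |
| Good practice during preparation and administration | 2.3.2.1 | Yes | No |
| Operators experienced in guided infiltration | 15 | Yes | No |
| Stop treatment on an allergic reaction | 5.4.1 | No | No |
| Unblinding for an allergic-type reaction | 4.8 | No | No |
| Recording and follow-up of adverse events | 8.4.4, 8.5.4 | No | No |

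Several provisions can act in time, but none is a written latex precaution. The planned number having the guided procedure is 150 of 150, and the number of latex-specific preventive steps in the criteria and technique is 0.

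**The case against.** The strongest case on the other side is that this is routine care. Recruitment follows the departments' ordinary referral (5.3), the teams have several years of experience in guided infiltration (15), and a clinician taking a history may well ask about latex. A protocol need not write out every such question. The allergy item also omits the ultrasound gel and Xylocaine, and Xylocaine is actually injected, so asking for latex alone can look selective. Most of this stands, and it is why the point is minor. It does not remove the gap: the protocol itself singles out latex in the cover as a hazard, and a named hazard deserves a matching line.

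Four stronger readings are tempting, and the documents do not support them:

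- *That the protocol obliges operators to use latex.* Section 4.2.2.2 prescribes no cover material. The statement about latex is descriptive and sits in the risk summary. An operator could choose a latex-free cover without departing from the technique.
- *That every safeguard comes too late.* The history, the investigator's discretion and good practice can all act before contact.
- *That a number of patients at risk can be given.* The documents contain no prevalence of latex allergy. Any figure would reflect only the value assumed, and the point does not need one.
- *That the authors had a systemic reaction in mind.* The gel reaction is called local and the latex reaction is not, but the two sentences are adjacent and linked. The difference in wording is too slight to carry that inference.

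**Conclusion.** The point holds as a minor gap in patient safety. The protocol says that the sterile cover uses latex and may cause a reaction, and a patient with known latex allergy is nevertheless eligible on the written criteria for a technique that specifies neither cover nor check. The general safeguards make harm unlikely.

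The conclusion rests on the criteria and the technique section, both of which are available in full. The consent pages and appendices are not, and either may mention latex. That would not alter what the criteria and technique say, but it does rule out claiming that the trial has no latex precaution anywhere.

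**What to change.** **Preferred.** Require a latex-free sterile probe cover in 4.2.2.2 and reword the latex sentence in 2.3.2.1 to match. This is one sentence in each place and excludes nobody.

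**If latex covers are kept.** Add known latex allergy to the allergy item in 5.2 and in the Summary. This is one short addition in each place and excludes only patients with that known allergy.

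**Cost.** The documents do not say whether latex-free covers are stocked at the three centers, so this should be confirmed first. Under 12.2, a substantial modification needs a favorable ethics committee opinion and ANSM authorization, and new consent if necessary. Whether this edit would count as substantial is not stated. It is therefore best carried with the next amendment rather than submitted alone.
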